### **7.8.3 Additional Efficacy Endpoint(s)**

Disease control rate (DCR) per investigator (CR+PR+SD) will be summarized with 2-sided 95% exact confidence intervals using the safety/mITT population. A sensitivity analysis of DCR per investigator will also be summarized using the Per-protocol population.

## **7.9 Pharmacokinetic/Pharmacodynamic Analysis**

### **7.9.1 Pharmacokinetic Analysis**

Pharmacokinetic analysis will be conducted using the PK population.

Serum concentrations of brentuximab vedotin (ADC) and total therapeutic antibody (TAb), and plasma concentrations of monomethyl auristatin E (MMAE) will be determined using validated assays.

Descriptive statistics (eg, number of patients, arithmetic mean, geometric mean, StdDev, median, percentage of coefficient of variation (%CV), minimum, and maximum) will be used to summarize serum concentrations of ADC and TAb, and plasma concentrations of MMAE at each prespecified time point in Cycle 1 through 16. The mean concentrations-time profiles of ADC, TAb, and MMAE will be plotted over time and in greater detail for Cycles 1 and 2. The complete set of the same data (Cycles 1-16 or up to the cycle where  $N \geq 3$ ) will also be plotted for ADC on a single plot. Similar plots will be provided for TAb and MMAE. Individual patient concentration data will be listed and plotted over time by cycle.

Noncompartmental analysis for the determination of PK parameters such as  $t_{max}$ ,  $C_{max}$ ,  $AUC_{21D}$ ,  $AUC_{\infty}$ ,  $t_{1/2z}$ , CL, and  $V_{ss}$  will be performed as data permit for ADC and TAb. The PK parameters of  $t_{max}$ ,  $C_{max}$ ,  $AUC_{21D}$ ,  $AUC_{\infty}$ , and  $t_{1/2z}$  will be estimated for MMAE. These parameters will be summarized by cycle. The summary statistics will consist of N, mean, StdDev, %CV, median, min, max, and geometric mean. Individual patient values of the parameters will be listed by cycle.

More exploratory plots may be presented in the CSR as needed.

### 7.9.2 Pharmacodynamic Analysis

Not applicable.

## 7.10 Other Outcomes

### 7.10.1 Immunogenicity Analysis

Immunogenicity will be summarized using the Immunogenicity population (Section 7.2.4). Descriptive statistics will be used to summarize patients in the following categories: ATA negative, transiently ATA positive, persistently ATA positive, low or high ATA titer, and negative or positive nATA.

- ATA Negative – defined as patients who do not have a confirmed positive ATA status in any postbaseline assessment.
- Transiently ATA positive – defined as patients who have confirmed positive ATA status in 1 or 2 postbaseline assessments.
- Persistently ATA positive – defined as patients who have confirmed positive ATA status in more than 2 postbaseline assessments.
- High ATA titer – defined as patients who have at least one postbaseline ATA titer  $>25$ .
- Low ATA titer – defined as patients whose postbaseline ATA titer numbers are all  $\leq 25$ .
- nATA negative – defined as patients who do not have positive nATA in any postbaseline ATA positive sample.
- nATA positive – defined as patients who have positive nATA in any postbaseline ATA positive sample.

ATA status, ATA titer and nATA will be listed by patient. ATA titer (high or low) and nATA status (nATA negative or positive) will also be tabulated for patients who are transiently or persistently ATA positive.

For effect of ATA and nATA on efficacy, the proportions of patients in CR and PR may be summarized within each ATA response status (negative, transiently positive, persistently positive) and nATA status by disease type. The same analysis may be repeated based on ATA titer (high,  $>25$ ; low,  $\leq 25$ ). In addition, patient level ATA and efficacy (overall response) data may be listed together.

For effect of ATA and nATA on safety, patient incidence of AEs (preferred term) by ATA response status (negative, transiently positive, persistently positive) and nATA status may be provided for both HL and sALCL. The same analysis may be repeated based on ATA titer (high, >25; low, ≤25).

CCI

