#### **10.3.16 Immunogenicity Measurements**

Blood samples for immunogenicity (in serum) assessments will be taken at prespecified time points as described in Table B ([Appendix A](#)). On dosing days, the blood samples for immunogenicity assessments must be collected before dosing.

Detailed information about the immunogenicity blood volume, blood sample collection, processing, storage conditions, and shipment will be provided in the Sample Management Plan and Laboratory Manual.

Positive ATA screening samples will be further tested for true positivity. Confirmed true positive ATA samples will be further characterized for neutralizing activity.

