### **5.2 Secondary Endpoints**

- CR rate.
- DOR.
- PFS.
- OS.
- B symptom resolution rate.
- Maximum observed plasma concentration ( $C_{max}$ ).
- Time to reach  $C_{max}$  ( $T_{max}$ ).
- Area under the plasma concentration-time curve from time 0 to infinity ( $AUC_{\infty}$ ).
- Presence of antitherapeutic antibodies (ATA) and neutralizing antitherapeutic antibodies (nATA) to brentuximab vedotin.

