## 7.0 METHODS OF ANALYSIS AND PRESENTATION

### 7.1 General Principles

In general, descriptive statistics (number of observations, mean, standard deviation [StdDev], median, minimum, and maximum) will be used to summarize continuous variables. Frequency and percentage will be used to summarize categorical variables. Time-to-event data will be analyzed using the Kaplan-Meier method and results will be summarized by the 25th, 50th (median), and 75th percentiles, if estimable, with associated 2-sided 95% confidence intervals, as well as the percentage of censored observations.

Means and medians will be presented to 1 more decimal place than the recorded data. The standard deviations (StdDev) will be presented to 2 more decimal places than the recorded data. Confidence intervals about a parameter estimate will be presented using the same number of decimal places as the parameter estimate.

Unless otherwise specified, safety and efficacy data will be summarized in the following 3 groups: patients with r/r HL only, patients with r/r sALCL only, all patients. Analyses pertaining to pharmacokinetics and immunogenicity will be summarized by treatment cycle at the prespecified time points.

The baseline value is defined as the value collected at the time closest to, but prior to, the start of study drug administration, unless otherwise specified. A windowing convention may be used to determine the analysis value for a given study visit for observed data analyses.

All available efficacy and safety data will be included in data listings and tabulations. Data that are potentially spurious or erroneous will be examined under the auspices of standard data management operating procedures. In general, there will be no imputation of missing data. For time-related endpoints, subjects who have no specified events will be censored as specified for each respective endpoint in Section 7.8. Imputation rules for missing dates of AEs and concomitant medications are detailed in Sections 7.1.3 and 7.1.4.

The primary analysis for the clinical study report including the primary and the secondary endpoints will be conducted when all patients have had the opportunity to receive 16 cycles of treatment and have had EOT assessments. The results will be summarized in the primary CSR. The final analysis will be conducted when all patients have had the opportunity to be followed for 18 months after EOT. These results will be summarized in the CSR Addendum.

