### 7.2.4 Immunogenicity Population

The Immunogenicity population consists of patients who receive at least 1 dose of brentuximab vedotin and have ATA status assessment at Baseline, and at least one postbaseline sample.

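### ATA and nATA categories use postbaseline samples only, so the tables may overstate treatment-emergent immunogenicity if any patient is ATA positive at baseline and stays positive without a titer rise

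*SAP*

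**What the plan says.** The secondary objective in both documents includes the immunogenicity of the drug. The endpoint is "Presence of antitherapeutic antibodies (ATA) and neutralizing antitherapeutic antibodies (nATA) to brentuximab vedotin" (SAP 5.2). To enter the Immunogenicity population a patient must be dosed and "have ATA status assessment at Baseline, and at least one postbaseline sample" (SAP 7.2.4). A baseline result is required; a negative one is not.

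SAP 7.10.1 then defines seven categories:

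- ATA negative: "defined as patients who do not have a confirmed positive ATA status in any postbaseline assessment".
- Transiently positive: "defined as patients who have confirmed positive ATA status in 1 or 2 postbaseline assessments".
- Persistently positive: "defined as patients who have confirmed positive ATA status in more than 2 postbaseline assessments".
- High titer: "defined as patients who have at least one postbaseline ATA titer" above 25. Low titer: every postbaseline titer at or below 25.
- nATA positive or negative: whether any ATA-positive sample after baseline is neutralizing.

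The general baseline rule is "The baseline value is defined as the value collected at the time closest to, but prior to, the start of study drug administration" (SAP 7.1). For ATA that is the Cycle 1 Day 1 predose sample in Table B of Protocol Appendix A. Protocol 10.3.16 describes confirmation as an assay step: "Positive ATA screening samples will be further tested for true positivity". Protocol 14.1.5 leaves the detail to the SAP. SAP 7.4 does not list ATA status among the baseline characteristics.

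**The concern.** The plan collects and requires the one result that separates pre-existing antibodies from those that arise on treatment, and then classifies patients without it. Take two patients, both confirmed positive at three or more visits after baseline. One was negative before the first dose. The other was positive before the first dose, at the same titer throughout. Both are reported as persistently positive. The high-titer cutoff is absolute, so an unchanged pre-existing titer above 25 also counts as high.

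What is at stake is the reading of the secondary result. A reader who wants to know how often the drug provokes antibodies would take the postbaseline rate as the answer, and it may not be. SAP 7.10.1 also allows summaries of response and of adverse events by ATA and nATA status. If these are produced, they would carry the same mixing. Elsewhere the SAP does use baseline: laboratory shifts and QTc changes are measured from it, and B symptom resolution is limited to patients with symptoms at baseline.

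**Working it through.** The documents state no ATA rate and no baseline ATA prevalence, so there is no figure of the plan's own to reproduce. The check has two parts.

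**1. How each type of patient is classified under SAP 7.10.1**

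| Baseline | After baseline | SAP category |
|---|---|---|
| Negative | Confirmed positive | Transient or persistent |
| Positive | Confirmed positive, titer rises | Transient or persistent |
| Positive | Confirmed positive, no titer rise | Transient or persistent |
| Positive | Never confirmed positive | ATA negative |

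The first three rows fall together. Only the third is not a response to the drug. Reading Table B as sampling at Cycles 2, 3, 5 and so on, a stable pre-existing antibody reaches three positive samples, and so becomes persistent, at about Cycle 5.

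**2. Size**

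Inputs: N = 30, the approximate planned total (SAP 6.0). Assumed for illustration: k = 3 baseline-negative patients who become positive, and b = 0 to 3 baseline-positive patients. Of these b, m are still confirmed positive after baseline and r of those m have a titer rise.

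- SAP postbaseline rate = (m + k)/N
- Treatment-emergent rate (induced plus boosted, all patients) = (k + r)/N
- Treatment-induced rate (baseline-negative denominator) = k/(N − b)

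| b | m | r | SAP rate | Treatment-emergent | Treatment-induced |
|---|---|---|---|---|---|
| 0 | 0 | 0 | 3/30 = 10.0% | 3/30 = 10.0% | 3/30 = 10.0% |
| 1 | 1 | 0 | 4/30 = 13.3% | 3/30 = 10.0% | 3/29 = 10.3% |
| 2 | 2 | 0 | 5/30 = 16.7% | 3/30 = 10.0% | 3/28 = 10.7% |
| 3 | 3 | 0 | 6/30 = 20.0% | 3/30 = 10.0% | 3/27 = 11.1% |
| 3 | 3 | 3 | 6/30 = 20.0% | 6/30 = 20.0% | 3/27 = 11.1% |
| 3 | 0 | 0 | 3/30 = 10.0% | 3/30 = 10.0% | 3/27 = 11.1% |

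On the common denominator, the SAP rate exceeds the treatment-emergent rate by (m − r)/N. That is 1/30 = 3.3 points for each patient who stays positive without a rise, and 3/30 = 10 points for three. This difference does not depend on k. Against the treatment-induced rate the direction is not fixed: the SAP rate is higher when m/b exceeds k/(N − b) and lower when it falls below, as in the last row.

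If the table is also split by disease, one such patient is 1/22 = 4.5 points in HL or 1/8 = 12.5 points in sALCL. The protocol's Study Summary points to separate analyses by disease unless otherwise stated. SAP 7.1 describes immunogenicity only by cycle and time point, so these two figures are conditional.

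**The case against.** The strongest defence is that the endpoint is presence of ATA, and the SAP categories measure presence after baseline as worded. Nothing in the SAP labels the rate as treatment-emergent. This stands, and it is why the present categories should be kept and supplemented. It does not remove the gap, because the objective concerns the immunogenicity of the drug and the SAP calls its three-level grouping an ATA response.

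Second, baseline results are not lost. SAP 7.10.1 lists ATA status, titer and nATA by patient, and SAP 7.1 summarizes immunogenicity by cycle at the planned time points, which on a plain reading include the predose sample. With about 30 patients, pre-existing cases could be traced by hand. This softens the point, but neither output reclassifies anyone in the category tables.

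Third, the summaries by response and by adverse events are optional, and antibody present on treatment, whatever its origin, is a defensible exposure for them. That is fair; the mixing there is a limit on interpretation.

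A reader might go further and infer that the reported rate is overstated, that it can only err upward, or that every baseline-positive patient inflates it. The documents support none of these. No baseline prevalence is given. A baseline-positive patient counts only with a confirmed positive sample after baseline, and one whose titer rises on treatment is a genuine response. With a baseline-negative denominator the SAP rate can be the lower one (10.0% against 11.1%).

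Text at the end of SAP 7.10.1 and of Protocol 14.1.5 is redacted and cannot be judged; the seven definitions themselves are visible.

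**Conclusion.** The point holds as a conditional one. The planned categories cannot separate an unchanged pre-existing antibody from one that develops on the drug, and that is true whatever the prevalence. The numerical effect exists only if at least one patient is positive at baseline and stays confirmed positive without a titer rise. In that case the postbaseline rate, read as treatment-emergent, is too high by 3.3 points per such patient. For 0 to 3 such patients, which is an assumption, the range is 0 to 10 points. The figures take all 30 planned patients as evaluable; with fewer, each patient weighs more. This is a descriptive secondary endpoint with no test or decision rule attached. The case for changing it rests on a clearer result at low cost, and the primary conclusions are not affected.

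**What to change.** In SAP 7.10.1:

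- Keep the present categories, labelled as postbaseline presence of ATA.
- Tabulate baseline ATA status in the Immunogenicity population.
- Add treatment-induced ATA: baseline negative with at least one confirmed positive sample after baseline. Denominator: baseline-negative patients.
- Add treatment-boosted ATA: baseline positive with a titer rise, the size of rise to be prespecified from the assay's titration. Denominator: baseline-positive patients.
- Report treatment-emergent ATA as induced plus boosted over all evaluable patients.
- Show baseline-positive patients without a rise in a separate row.
- Apply transient and persistent to treatment-induced cases.

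If the optional summaries by response and adverse events are produced, show them by the same groups.

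The cost is SAP wording, a few more table rows, and a titer-rise threshold that must be set before results are seen. The headline rate may come out lower. No new sample is needed, because the predose sample is already collected and required. If no patient is positive at baseline, the added rows show zero and confirm that the postbaseline and treatment-emergent rates agree.

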## 7.11 Safety Analysis

Safety will be evaluated by the incidence of treatment-emergent AEs (TEAEs), severity and type of AEs, and by changes from baseline in the patient's vital signs, neurotoxicity assessment, ECGs, and clinical laboratory results. Exposure to study drug and reasons for discontinuation will also be tabulated.

These analyses will be performed using the safety/mITT population.

### 7.11.1 Adverse Events

AEs will be tabulated according to the Medical Dictionary for Regulatory Activities (MedDRA) Version 19.0 or higher by system organ class, high-level terms, preferred terms and severity. AEs with missing start and/or end dates will be imputed according to rules specified in Section 7.1.3. TEAEs are defined as any AEs that occur after administration of the first dose of brentuximab vedotin and up through 30 days after the last dose. Patients who experience the same AE more than once will have that event counted only once within each system organ class, once within each high-level term, and once for each preferred term. AEs will be summarized and will include the following categories:

- TEAEs.
- Drug-related TEAEs.
- Grade 3 or higher TEAEs.
- Grade 3 or higher drug-related TEAEs.
- TEAEs resulting in study drug discontinuation.
- SAEs.
- AEs of peripheral neuropathy identified by the broad search MedDRA SMQ “Peripheral neuropathy”.

Treatment-emergent AEs will be tabulated by system organ class, high-level term and preferred term. The most commonly reported treatment-emergent AEs (ie, those events reported by ≥10% of all patients) will be tabulated by preferred term. Additional analyses of peripheral neuropathy may also be presented.

#### *7.11.1.1 Serious Adverse Events*

The number and percentage of patients experiencing at least 1 treatment-emergent SAE will be summarized by MedDRA (Version 19.0 or higher) primary system organ class, high-level term, and preferred term. Drug-related SAE assessed by the investigator will be summarized similarly.

In addition, a by-subject listing containing all SAEs will be presented, regardless of treatment-emergent AE status.

#### *7.11.1.2 Peripheral Neuropathies*

Peripheral Neuropathy (PN) is defined by the peripheral neuropathy SMQ broad search. The incidence of treatment-emergent PN and treatment-emergent drug-related PN will each be summarized by preferred term and severity. The incidence of peripheral motor neuropathy will also be calculated. Time to onset, resolution and improvement of PN events will be summarized. Individual plot by preferred term for treatment-emergent peripheral neuropathy (SMQ) may be presented.

#### *7.11.1.3 Deaths*

A by-subject listing of the deaths will be presented. All deaths occurring on-study and during follow-up will be displayed (regardless of treatment-emergent AE status). On-study death is defined as a death that occurs between the first dose of brentuximab vedotin and 30 days after the last dose.

#### *7.11.1.4 Adverse Events Resulting in Discontinuation of Study Drug*

AEs resulting in discontinuation of study drug will be presented in a by-patient listing and also in a summary table by system organ class, high-level term and preferred term.

### **7.11.2 Clinical Laboratory Evaluations**

Descriptive statistics for the actual values of clinical laboratory parameters (and/or change from baseline in clinical laboratory parameters) will be presented for all scheduled measurements over time. Mean laboratory values over time will be plotted for key laboratory parameters.

If a patient has repeated laboratory values for a given time point, the value from the latest evaluation will be used. If the report lab values contain a nonnumeric qualifier, eg, > or <, the given numeric portion will be used in summary statistics.

The parameters to be analyzed are as follows:

- Hematology: Red blood cells, hemoglobin content, hematocrit, white blood cells, platelets, differential white blood cells (neutrophils, eosinophils, basophils, lymphocytes, monocytes), reticulocyte.
- Serum chemistry: Sodium, potassium, chloride, albumin, calcium, phosphorus, glucose, BUN, uric acid, creatinine, total bilirubin, AST, ALT, ALP, LDH, GGT, HbA1c, total cholesterol, triglycerides, TSH, FT3, FT4.

- Coagulation: INR, PT, APTT.

Shift tables for laboratory parameters will be generated based on changes in NCI CTCAE grades from Baseline to the worst postbaseline value.

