##### **Chemistry A**

- Screening period: Days -14 to 0; screening testing within 3 days of study dose on Day 1 of Cycle 1 may be substituted for testing on Day 1 of Cycle 1.
- Cycles 1 and 2: Days 1, 8, and 15; the testing on Day 1 of each cycle is to be performed within 3 days before study treatment and the testing on Day 1 of Cycle 2 is to be performed within 1 day before study treatment.
- Cycle 3 and subsequent cycles: Days 1 and 15; the testing on Day 1 of each cycle is to be performed within 1 day before study treatment.
- Safety follow-up period: on the 30th day ( $\pm 7$  days) after the last dose of brentuximab vedotin.

Samples of glucose must be taken under fasting conditions (at least 4 hours after a meal) at screening and on Day 1 of Cycle 1. At other time points, although fasting levels (at least 4 hours after a meal) should be measured as a rule, nonfasting levels are also permitted; if a nonfasting level is measured, meal times must be recorded on the source document.

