##### **Chemistry B**

- Screening period: Days -14 to 0.
- Safety follow-up period: on the 30th day ( $\pm 7$  days) after the last dose of brentuximab vedotin.

Samples of total cholesterol and triglycerides must be taken under fasting conditions (at least 4 hours after a meal) at screening. At other time points, although fasting levels (at least 4 hours after a meal) should be measured as a rule, nonfasting levels are also permitted; if a nonfasting level is measured, meal times must be recorded on the source document.

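### Baseline glucose and lipids must be fasting but later samples need not be, and the worst-value shift table ignores the difference, so permitted nonfasting samples can inflate apparent glucose shifts

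*SAP*

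**What the plan says.** **Baseline samples.** Protocol 10.3.10.1, Chemistry A: "Samples of glucose must be taken under fasting conditions (at least 4 hours after a meal) at screening and on Day 1 of Cycle 1". Chemistry B: "Samples of total cholesterol and triglycerides must be taken under fasting conditions (at least 4 hours after a meal) at screening". SAP 7.1 defines baseline as the last value before study drug starts. If the protocol is followed, baseline glucose and lipids are therefore fasting values.

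**Later samples.** The default is still fasting: "fasting levels (at least 4 hours after a meal) should be measured as a rule". The same sentence then makes an exception: "nonfasting levels are also permitted; if a nonfasting level is measured, meal times must be recorded on the source document". Chemistry B has the same default and exception for lipids, and the footnotes to Table 10.a and to the Schedule of Events repeat both rules.

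**Analysis.** SAP 7.11.2 lists glucose, total cholesterol and triglycerides among the parameters. It summarises actual values and/or change from baseline at scheduled measurements, and adds: "Shift tables for laboratory parameters will be generated based on changes in NCI CTCAE grades from Baseline to the worst postbaseline value". Protocol 14.1.7 plans the same shift tables. Neither document says how nonfasting values are to be flagged, separated or excluded, and neither says that fasting status enters the eCRF.

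**The concern.** The two ends of the comparison are not taken under the same conditions. The baseline end must be fasting and the postbaseline end need not be. A nonfasting sample complies with the protocol, so a review of deviations would not remove it, and SAP 7.1 puts all available safety data into the tabulations.

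Taking the worst value adds to this for glucose. An occasional nonfasting sample hardly moves a visit mean, but a maximum over many visits is sensitive to a single high value. If a meal raises glucose (the documents do not say by how much), the effect on the shift is upward.

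Clinical laboratory values are part of the primary safety endpoint (Protocol 6.1), and the study has one arm. No comparison group would show how much of an apparent shift comes from meals. A reader of the glucose shift table could not tell a change on treatment from a change in sampling conditions.

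**Working it through.** The plan states no figure on this point, so there is none to reproduce. The check counts the scheduled samples and then sees how often a nonfasting one could enter the maximum.

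**Step 1. Scheduled postbaseline glucose samples (Chemistry A).** The schedule is "Cycles 1 and 2: Days 1, 8, and 15", then "Cycle 3 and subsequent cycles: Days 1 and 15", then one sample at safety follow-up. Cycle 1 Day 1 is a predose sample and counts as baseline.

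- 16 cycles: 2 (Cycle 1) + 3 (Cycle 2) + 2 × 14 (Cycles 3 to 16) + 1 (follow-up) = 34.
- 8 cycles: 2 + 3 + 2 × 6 + 1 = 18.

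**Step 2. Scheduled postbaseline lipid samples (Chemistry B).** After screening there is one: "Safety follow-up period: on the 30th day". With a single value there is nothing for a worst-value rule to choose from, unless unscheduled samples are taken. What remains for lipids is a fasting baseline set against a possibly nonfasting follow-up.

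**Step 3. Chance of at least one nonfasting glucose sample.** Let q be the chance that a postbaseline sample is nonfasting. The documents do not give q, so a range is assumed, with samples treated as independent. For m samples the chance is 1 − (1 − q)^m.

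| Assumed q | m = 18 (8 cycles) | m = 34 (16 cycles) |
|---|---|---|
| 2% | 30.5% | 49.7% |
| 5% | 60.3% | 82.5% |
| 10% | 85.0% | 97.2% |

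**Step 4. From exposure to a shift.** A nonfasting value changes the table only if it crosses a CTCAE grade and is worse than every fasting value in the same patient. Let r be the share of nonfasting samples that cross a grade. The documents do not give r, and they do not reproduce the grade limits. Over 34 samples, the chance that at least one nonfasting value crosses a grade is 1 − (1 − qr)^34:

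- q = 5%, r = 1%: 1 − 0.9995^34 = 1.7%
- q = 10%, r = 10%: 1 − 0.99^34 = 28.9%
- q = 20%, r = 20%: 1 − 0.96^34 = 75.0%

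These figures overstate the number of added shifts for a given q and r, because some patients will also have a fasting value at the same grade. For lipids, with one sample, the chance is q × r. It runs from 0.05% (5% × 1%) to 4% (20% × 20%).

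The range in Step 4 is too wide to serve as an estimate. It shows that the effect could be negligible or large, and that the plan has no means of telling which.

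**The case against.** Several stronger readings are tempting, and the documents do not support them.

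- **That meal effects will be reported as treatment-related.** The shift tables are descriptive. Relatedness is an investigator judgement made for each adverse event (Protocol 11.2), and a laboratory value becomes an adverse event only if it leads to action or is judged clinically significant (Protocol 11.1.2).
- **That nonfasting sampling will be common.** Fasting stays the default after baseline, and the share of exceptions is unknown.
- **That lipids suffer the same selection as glucose.** They do not, by Step 2.
- **That the percentages in Step 3 are rates of false shifts.** They are the chance of having any nonfasting sample.
- **That hyperglycemia is an established signal at this dose.** The Grade 3 hyperglycemia counted among dose-limiting toxicities in the first-in-human study occurred at 2.7 mg/kg; this study gives 1.8 mg/kg. Hyperglycemia is not among the common phase 2 events in Protocol 4.1.4 or the risks in Protocol 4.1.5.
- **That the eCRF lacks a fasting field.** The form is not among the documents. All that is known is that meal times must go in source.

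It can also be argued that the worst value regardless of meals is the inclusive choice for safety, and that removing nonfasting values from the main table could hide a genuine high reading. That argument stands, and the fix below respects it. HbA1c has no fasting condition and gives some independent evidence, but it is scheduled only at screening and safety follow-up, so it cannot sort individual on-treatment glucose values. The SAP rule that the latest repeat is used helps only where a repeat was taken for the same time point.

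None of this supplies the missing rule. The exception is expressly permitted, its frequency is not limited, and the analysis does not distinguish its results.

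**Conclusion.** The point holds as a low-severity gap in laboratory reporting. If the plan is followed as written, permitted nonfasting samples can bias apparent on-treatment glucose shifts upward, and a single-arm study gives no comparison that would reveal it. For triglycerides and total cholesterol, the problem is limited to one possibly mismatched follow-up sample.

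The count of 34 samples comes from the protocol schedule for a patient who completes 16 cycles; patients who stop earlier have fewer. The exposure figures rest on assumed nonfasting shares and independence between samples. The number of false grade shifts cannot be established from the documents. No efficacy result, sample size or relatedness assessment depends on this point.

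**What to change.** 1. Ensure that fasting status (yes/no, using the protocol's own 4-hour definition) is captured in the eCRF for each glucose and lipid sample, if it is not already.
2. In SAP 7.11.2, keep the worst-value shift table on all samples, so that no safety value drops out of view, and flag nonfasting values in it and in the listings.
3. Add a fasting-only change-from-baseline and shift table for glucose, triglycerides and total cholesterol, labelled as the like-for-like comparison.

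The cost is one data field, a short addition to the SAP and one extra table. No extra sampling is needed, and meal times for nonfasting samples are already required in source. The fasting-only table will hold fewer values than the all-samples table, and it should report how many were left out.
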